## **H. Incidence of Emergent Rhythm Abnormality (Arrhythmias)**

Based on the primary endpoint of rhythm abnormalities and available data, incidence of emergent rhythm abnormalities will be analyzed.

Subjects will be supplied with an e-Patch to monitor heart rhythm for continuous 14 days during the screening period. Clinically significant rhythm abnormalities during the screening period will result in exclusion from randomization on the basis of exclusion criteria 12 (page 37 of Protocol Amendment 3). Continuous telemetry monitoring will start as soon as practicable after hospital admission on Day 1 and prior to the treatment. It will continue until 48 hours after the end of study drug infusion on Day 3.

The percentage of emergent clinically significant arrhythmias detected by telemetry will be compared, both overall and on a per day basis following the administration (i.e. 0-24 hours and 24-48 hours), between each treatment group and placebo and will be presented in a summary table.

A listing will be generated for all subjects with incidence of rhythm abnormality.

## **I. Prior Medications or Concomitant Medications**

Any medication, vaccine, or therapy (including over-the-counter or prescription medicines, vitamins, and/or [herbal] supplements) that a subject receives within 30 days before informed consent, or receives during the study, must be recorded in the eCRF along with the reason for use, the dates of administration including start and end dates, and the dosage information including dose and frequency.

Prior Medications (PMs) are defined as any medication that starts and stops before Day 1 (IP administration day).

Concomitant Medications (CMs) are defined as any medication that:

- Starts prior to Day 1 and continues after Day 1
- Starts between Day 1 and early termination visit or end of study visit

Medications will be coded using the Sep 2019 version of WHO Drug. Prior medications and Concomitant Medications will be summarized separately by treatment group and overall, and organized to display the Anatomical Therapeutic Chemical (ATC) Class of each coded medication and, within that, the Preferred Term (PT) of the coded medication. The summary tables will display counts and percentages of subjects who reported at least one prior or concomitant medication in each represented PT. Prior medications that ended more than 30 days before the informed consent date will not be included in the summary table.

A by-subject listing will be presented with verbatim term given by the investigator, PT, ATC, indication (for adverse event, medical history, or prophylaxis), dose and units, frequency, route of administration, and whether it is prior medication or concomitant medication. For prior medications, the number of days between the medication's end date and the informed consent date will be displayed, and medications that ended more than 30 days before informed consent will be flagged. Within each subject, medications will be sorted by descending frequency of ATC and Preferred Term.

## **VIII. Pharmacokinetic Analyses**

The analyses described in this section will be performed at CR Medicon.

### **A. PK Data Handling**

The following data handling conventions apply to computations of PK concentration descriptive statistics:

- Observed concentrations that are below the lower limit of quantitation (BLQ) will be set to 0. The calculated mean concentrations are used in overlaid mean ( $\pm$  SD) concentration time profiles.
- If the calculated mean concentration is BLQ, the mean value shall be reported in the outputs as 0, SD and CV% shall be reported as ND (not determined). Min, median, and max may be reported. If any of these values are BLQ, it shall be reported as less than the lower limit of quantitation (< LLOQ) value.

The following data handling conventions apply to PK parameter calculation and individual serum concentration-time profiles.:

- Observed concentrations that are BLQ will be assigned a value of zero if they are prior to  $C_{max}$ . Observed concentrations of BLQ that occurs after  $C_{max}$  will be set to missing.
- The PK parameters for JK07 will be listed and included in the parameter summaries and statistical analyses if the predose concentration value of serum JK07 is not greater than 5% of  $C_{max}$  in the profile. If the predose concentration value of serum JK07 is greater than 5% of  $C_{max}$  in the profile, the profile will be reviewed in conjunction with JK07 serum concentrations measured at other timepoints prior to dosing on a case-by-case basis to evaluate if exclusion of data is warranted.
- The predose (within 30 minutes prior to start of infusion) value will serve as concentration at time 0 hour.
- Missing postdose values will be treated as missing and evaluated for potential impacts on PK (e.g., around  $C_{max}$ ) and exclusions may be warranted for affected parameters prior to data analysis.

## B. Calculation of PK Parameters

PK parameters for serum JK07 will be estimated by NCA methods using actual elapsed time from start of the IV infusion. A minimum of 4 quantifiable after dose concentrations will be required for all calculations.

If appropriate and feasible, the PK parameters listed in [Table 2](#) will be calculated but not limited to for serum JK07 concentrations obtained from PK Evaluation Population:

**Table 2: Parameters for Pharmacokinetic Analysis**

PK Parameters	Definition
$C_{max}$	Maximum concentration obtained directly from the observed concentration versus time data.

PK Parameters	Definition
$t_{max}$	Time to $C_{max}$ .
$AUC_{(0-inf)}$	Area under the serum concentration-time curve from time zero extrapolated to infinity, calculated by linear up/log down trapezoidal summation. If the percentage of AUC obtained by extrapolation is greater than 20%, $AUC_{(0-inf)}$ and related parameters (CL and $V_z$ ) will be listed but not included in any summaries or inferential analyses.
$AUC_{(0-last)}$	Area under the serum concentration-time curve from time zero to the time of the last quantifiable concentration, calculated by linear up/log down trapezoidal summation.
CL	Systemic clearance.
$V_z$	Volume of distribution.
$t_{1/2}$	Terminal half-life; a minimum of 3 points will be used for estimation.
$\lambda_z$	Terminal rate constant; if $Rsq (adj)$ is $<0.800$ , then $\lambda_z$ , $t_{1/2}$ , and related parameters will be listed but not included in any summaries or inferential analyses

In addition to the PK parameters presented above, dose normalized exposure parameters  $C_{max}$  and  $AUC_{(0-inf)}$  (or  $AUC_{(0-last)}$  if  $AUC_{(0-inf)}$  is not calculable in most subjects) will also be calculated. The lower and upper limits on time ( $\lambda_z_{lower} / \lambda_z_{upper}$ ) for the data used in the calculation of  $\lambda_z$ , the numbers of points (No\_points\_  $\lambda_z$ ) used in the calculation of  $\lambda_z$  and the  $Rsq (adj)$  will also be listed.

Calculated individual PK parameters of JK07 will be listed and descriptively summarized by active treatment and cohort for the PK evaluation population.

### C. Statistical Analysis of PK Concentration Data

Individual observed serum concentration-time data for JK07 will be listed. Serum concentration of JK07 will be summarized using descriptive statistics by active treatment and cohort at scheduled time point for the PK evaluation population. Summary statistics including the number of observations (n), mean, SD, %CV, min, median, max, number of values below the lower limit of quantitation (n\_BLQ), Geom. Mean and Geom. %CV will be calculated for all nominal concentration time points. All individual BLQ concentration values will be presented as 'BLQ' in the concentration tables and footnoted accordingly.

JK07 serum concentration-time profiles will be graphically displayed by active treatment and cohort on linear and semilogarithmic scales, as appropriate. Plots of individual values versus actual time grouped by active treatment and cohort (one plot for each cohort)

will be presented. Plots of overlaid mean ( $\pm$  SD) concentration versus nominal time grouped by active treatment and cohort will also be presented.

#### D. Statistical Analyses of PK Parameters

PK parameters for each subject in the PK parameter population will be listed and summarized using descriptive statistics by active treatment and cohort. Summary statistics including n, mean, SD, %CV, min, median, max, Geom. Mean and Geom. %CV will be calculated for serum JK07 PK parameters (except for  $t_{max}$  which will only be presented as min, median and max).

Scatter plots of individual values and Geom. Mean of PK parameters,  $AUC_{(0-inf)}$  (or  $AUC_{(0-last)}$  if  $AUC_{(0-inf)}$  is not calculable in most subjects) and  $C_{max}$  as well as dose-normalized exposure parameters versus dose will be presented.

The proportionality of the PK parameters such as  $C_{max}$  and  $AUC_{(0-inf)}$  (or  $AUC_{(0-last)}$  if  $AUC_{(0-inf)}$  is not calculable in most subjects) over the administered dose range may also be explored graphically using a power model by confidence interval criteria. This approach will be based on a linear relationship between the natural log-transformed PK parameter and log-transformed dose:

$$\ln(\text{parameter}) = \beta_0 + \beta_1 \cdot \ln(\text{dose})$$

Where,  $\beta_0$  is the intercept and  $\beta_1$  is the slope of the line.

The assessment involves a test of whether a 90% confidence interval of  $\beta_1$  fits within a pre-specified critical interval, normalized for the dose range, i.e. whether

$$1 + \frac{\ln(\theta_L)}{\ln(r)} < \beta_1 < 1 + \frac{\ln(\theta_H)}{\ln(r)}$$

where  $\theta_L$  is the lower bound of the critical interval,  $r$  is the ratio of the highest dose to the lowest dose, and  $\theta_H$  is the upper bound of the critical interval. For this analysis  $\theta_L$  and  $\theta_H$  will be chosen as 0.5 and 2.0^1, respectively, to reflect a practical assessment of approximate dose-proportionality. 90% confidence interval of  $\beta_1$  will be summarized.

In the case that dose-proportionality is not confirmed over the entire dose-range, linearity over a smaller dose range will be assessed.

A sample of SAS implementation code for analyzing dose proportionality is shown below:

```
* Assess the dose proportionality by using a power model
  with applying natural log transformation on parameters
  (AUC and Cmax) and dose;
proc mixed data=pk_dataset;
  class usubjid;
  model logpkval=logdose / ddfm=kr;
* logpkval and logdose correspond to the log transformed
  value of the PK parameter and dose, respectively;
  random usubjid;
* apply subject as random effect;
  estimate 'mean slope of logdose' logdose 1 /cl alpha=0.1;
* calculate 90% Confidence Interval for mean slope of logdose;
  ods output estimates=estimate;
run;
```

## IX. Exploratory Pharmacodynamic Analysis

The analyses described in this section will be performed at CR Medicon.

### A. Analysis of 2-dimensional Transthoracic Echocardiography (2D-TTE) and Biomarkers

Same as the non-PK/PD analysis, the subjects who received placebo will be combined into one treatment group for purposes of analysis. The baseline measure will be defined as the last non-missing measure prior to initiation of IP. Change from baseline will be calculated as post baseline value subtracted by value at baseline. Exploratory inferential comparisons to placebo may also be performed.

Results of the 2D-TTE and biomarkers and their change from baseline values (as applicable) will be listed and descriptively summarized by treatment at scheduled time point (details are in the Protocol JK07.1.01 – Amendment 3 Section 1.3, Schedule of Activities) Summary statistics including n, min, max, mean, SD and median will be calculated.

Values outside of the laboratory's reference range (i.e., those with low or high values) will be flagged in the listings if applicable.

### B. Potential Effect of JK07 on QTc Prolongation

For the analysis of a serum concentration to QT (C-QT) relationship, ECG values will be combined with the subject-specific, time-matched JK07 concentration assessments.

### **1. Baseline**

The baseline value will be derived as mean from triplicate ECG recordings measured prior to initiation of IP. The baseline QTc should be included in the C-QTc model as a covariate.

### **2. Correction Formulae**

Fridericia corrected QT interval ( $QT_{cF}$ ) =  $QT/RR^{1/3}$ , RR refers to a normalized heart rate of 60 bpm.

$\Delta QT_{cF}$  refers to the predose baseline-corrected  $QT_{cF}$  interval and  $\Delta\Delta QT_{cF}$  refers to the  $\Delta QT_{cF}$  interval corrected for placebo.

### **3. Exploratory Plots of Model**

Subjects who received placebo will be combined into 1 treatment group for purposes of analysis. Basic assumptions can efficiently be evaluated using simple graphics to show that:

- No Effect of JK07 on change of HR

Plot of mean change from baseline in heart rate ( $\Delta HR$ ) and 2-sided 90% CIs vs. time by treatment.

Plot of mean change from baseline placebo-adjusted heart rate ( $\Delta\Delta HR$ ) and 2-sided 90% CIs vs. time by treatment.

- $QT_{cF}$  interval is independent of HR

Scatterplot of  $QT_{cF}$  and RR intervals by treatment with linear regression line and 90% confidence interval.

- No time delay between drug concentrations and  $\Delta QT_{cF}$

Plots of mean  $\Delta\Delta QT_{cF}$  and drug concentration and 2-sided 90% CIs vs. time by treatment.

Plot of mean  $\Delta\Delta QTcF$  and 2-sided 90% CIs vs. concentration connected in temporal order by treatment.

A delay of mean  $\Delta QTcF$  with respect to the  $C_{max}$  of the JK07 of  $> 1.5$  hours is considered an indication of hysteresis unless all values of  $\Delta QTcF$  are  $< 5$  msec.

- Linear C-QTcF relationship

Scatter plot of paired  $\Delta QTcF$  vs. concentration data with smooth line and 90%confidence intervals and linear regression line.

#### 4. QTcF-Concentration Model Analysis

If the exploratory plots indicate the modeling assumptions are met, an exploratory evaluation of C-QT relationship will be conducted using a linear mixed effects model, with the drug-free-corrected (i.e., predose-corrected) change from baseline in QTcF as the response variable. Independent variables will include the fixed effects time-matched JK07 serum concentration, treatment indicator (treatment = 1 for subjects receiving JK07, and 0 otherwise), time point as a categorical variable, influence of baseline on intercept and random effects for subject and time matched JK07 serum concentration.

$$\begin{aligned}\Delta QTc_{ijk} &= (\theta_0 + \eta_{0,i}) + \theta_1 TRT_j + (\theta_2 + \eta_{2,i}) C_{ijk} + \theta_3 TIME_k + \theta_4 (QTc_{i,0} - \bar{QTc}_0) \\ \Delta QTc_{ijk} &= (\theta_0 + \eta_{0,i}) + \theta_1 TRT_j + (\theta_2 + \eta_{2,i}) C_{ijk} + \theta_3 TIME_k + \theta_4 (QTc_{i,0} - \bar{QTc}_0)\end{aligned}$$

Where:

$\Delta QTc_{ijk}$  is the change from baseline in QTc for subject i in treatment j at time k.

$\theta_0$  is the population mean intercept in the absence of a treatment effect.

$\eta_{0,i}$  is the random effect associated with the intercept term  $\theta_0$ .

$\theta_1$  is the fixed effect associated with treatment  $TRT_j$  (0 = placebo, 1 = active drug).

$\theta_2$  is the population mean slope of the assumed linear association between concentration and  $\Delta QTc_{ijk}$ .

$\eta_{2,i}$  is the random effect associated with the slope  $\theta_2$ .

$C_{ijk}$  is the concentration for subject i in treatment j and time k.

$\theta_3$  is the fixed effect associated with time.

$\theta_4$  is the fixed effect associated with baseline  $QTc_{ij0}$ .

$\overline{QTc_0}$  is overall mean of  $QTc_{ij0}$ , i.e., the mean of all the baseline (= time 0) QTc values. It is assumed the random effects are normally distributed with mean [0,0] and an unstructured covariance matrix G, whereas the residuals are normally distributed with mean 0 and variance R.

Estimation of model-derived  $\Delta\Delta QTc$  at concentrations of interest

Estimated mean  $\Delta\Delta QTc(C) = \bar{\theta}_1 + C\bar{\theta}_2$

Estimated SE =  $\sqrt{var(\hat{\theta}_1) + C^2 var(\hat{\theta}_2) + 2C cov(\hat{\theta}_1, \hat{\theta}_2)}$

90% CI = Estimated mean  $\Delta\Delta QTc(C) \pm t(0.95, df) \times \text{Estimated SE}$

The upper bound of the 2-sided 90% CI will be compared with the regulatory threshold of 10 ms.

SAS code used for linear mixed effects model as below:

```
PROC MIXED DATA=dataset;
  CLASS time subjid trt;
  /* trt=1 for active and trt=0 for placebo */
  MODEL dQTc = trt conc time predoseQTc/DDFM=KR;
  /* conc=Concentration*/
  RANDOM intercept conc/SUBJECT=subjid type=UN;
RUN;
```

## 5. Model Evaluation

To assess the appropriateness of a priori choice of linear model between  $\Delta QTcF$  and serum concentration, the following goodness of fit plot will be assessed:

- Quantiles of concentrations and  $\Delta QTcF$  overlaid with slope of final model.

Model parameters are to be presented in tabular format showing the estimate, standard error of the estimate, *p* value and 90% confidence interval.

## **6. Model development for adapted C-QTc models**

If the exploratory plots indicate the modeling assumptions are not met, additional modeling steps are recommended to determine objectively the appropriate C-QT model. When apparent differences in the time course and/or distribution of HR between on- and off-drug conditions are observed in exploratory plots, other approaches to evaluate QT/QT should be considered. In this case, one stand-alone modeling analysis plan (MAP) needs to be generated.

## **X. Exploratory Biomarkers**

The analyses described in this section will be performed at CR Medicon.

The analysis of exploratory biomarkers will be performed using the exploratory PD/biomarker evaluation population. Descriptive summary statistics will be reported for the actual observed and change from baseline for the following biomarkers (hsCRP, troponin-I or hs-troponin T, CPK, CPK-MB, lactate dehydrogenase, NT-proBNP and total BNP) by treatment groups and visits (Day 1 pre-infusion, Day 2, 7, 15, 30, 60, 90, 135, 180 (or end of study visit)). Baseline values are those obtained at pre-infusion on Day 1.

Separate summaries will be produced for results collected by Local labs (in the EDC system) and by Central labs (by Q vendor).

Exploratory biomarker results will be listed.

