## 8.8 Biomarkers

- Collection of samples for biomarker research is a component of the safety monitoring for this study and also an exploratory part of this study. Samples will be tested for predictive muscle and inflammatory biomarkers to evaluate their association with the observed clinical responses to JK07. The following samples for the safety and exploratory muscle and inflammatory biomarkers will be collected from all subjects in this study as specified in the SoA:
  - Additional biomarkers: hsCRP, troponin-I and/or hs-troponin T, CPK, CPK-MB, and lactate dehydrogenase.
  - Exploratory biomarkers: NT-proBNP, total BNP
- Venous blood samples of approximately 10 mL will be collected at several time points as per the SoA (Table 1) and Appendix 3, Table 15, for measurement of exploratory biomarkers. Instructions

for the collection and handling of biological samples will be provided by the Sponsor in a separate Laboratory Manual.

- Serum biomarker samples will be analyzed by the Sponsor designated clinical laboratory (Q Solutions).

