## Appendix 3 Clinical Laboratory Tests

- Blood will be collected for local laboratory assessments at times when the central laboratory results are not expected to be available in time for either study treatment administration and/or response evaluation. The local laboratory results must be entered into the eCRF. [Table 14](#) identifies local laboratory assessments scheduled for this study (and the specific timepoints for assessment) but may not be fully comprehensive in cases where additional safety follow-up deemed appropriate by the Investigator. Table 15 identifies blood draw requirements for central lab assessment.
- Protocol-specific requirements for inclusion or exclusion of subjects are detailed in [Section 5.0](#) of the protocol.
- Additional tests may be performed at any time during the study as determined necessary by the Investigator or required by local regulations.
- All results must be recorded in the eCRF.

**Table 13** Protocol-required Safety Laboratory Assessments

Laboratory Assessments	Parameters	
Hematology	Platelet Count	WBC Count with Differential:
	RBC Count	Neutrophils
	Hb	Lymphocytes
	Hct	Monocytes
	RBC Indices:	Eosinophils
	MCV	Basophils
	MCH	
	MCHC	
	%Reticulocytes	
Clinical Chemistry	ALT/ SGPT	
	Albumin	Phosphate
	ALP	Potassium
	AST/ SGOT	Total bilirubin (conjugated and unconjugated if clinically indicated)
	BUN	Direct bilirubin
	Calcium	Total Cholesterol
	Carbon dioxide (bicarbonate)	Total Protein
	Chloride	Triglycerides
	Creatinine	Uric acid
	Fasting Glucose	
	GGT	
	HDL Cholesterol	
	LDL Cholesterol	
Coagulation	INR	aPTT
	Prothrombin time (PT)	Fibrinogen
Additional biomarkers	CPK a	hs CRP
	CPK-MB a	Troponin I b
	hs Troponin T b	LDH
Urinalysis	Leucocytes	RBCs
	Protein	pH
	Bilirubin	Nitrite
	Urobilinogen	Specific gravity
	Ketones	Glucose
	Microscopy (if clinically indicated)	Myoglobin
Viral serology	HIV I and II	HCV
	HBsAg	HBV PCR
Drugs of abuse and alcohol c		
Thyroid profile	TSH Total T4 T3	T4 Total T3
Glycosylated hemoglobin	HbA1c	
Other screening tests	Urine $\beta$ -hCG pregnancy test (as needed for subjects of childbearing potential) Study-required laboratory assessments will be performed by local and central laboratories. Table 14 shows the Safety Laboratory Assessments Performed by Local Laboratories. Table 15 lists the protocol required local laboratory collections for Central Laboratory Analysis.	

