**Table 14 Schedule of Protocol-required Safety Laboratory Assessments Performed by the Local Laboratory**

Day	Time (hours)	Panel	Comment
Screening	No more than 45 days prior to IP administration	Chemistry a	
		Hematology	
		Coagulation	
		Additional biomarkers	CPK b , CPK-MB b , Troponin I and/or hs Troponin T, hsCRP, LDH
		HIV/HBV/HCV	
		β-hCG (blood sample)	
		Urinalysis	
		Thyroid profile	
Day 1 prior to IP administration	Upon admission	Chemistry a	
		Hematology	
		Coagulation	
		Additional biomarkers	CPK b , CPK-MB b , Troponin I and/or hs Troponin T, hsCRP c , LDH
		Glucose	Fingerstick
		Urinalysis	Including urine-based pregnancy dipstick for pre-menopausal women
Day 1 postdose	End of infusion	Glucose	Fingerstick
	4	Additional biomarkers	CPK b , CPK-MB b , Troponin I and/or hs Troponin T, hsCRP c , LDH
		Glucose	Fingerstick
	8 hours postdose	Additional biomarkers	CPK b , CPK-MB b , Troponin I and/or hs Troponin T, hsCRP c , LDH
		Glucose	Fingerstick
	12 hours postdose	Additional biomarkers	CPK b , CPK-MB b , Troponin I and/or hs Troponin T, hsCRP c , LDH
		Glucose	Fingerstick
2	24 hours postdose	Chemistry a	
		Hematology	
		Coagulation	
		Additional biomarkers	CPK b , CPK-MB b , Troponin I and/or hs Troponin T, hsCRP c , LDH
		Glucose	Fingerstick
		Urinalysis	
3	48 hours postdose	Additional biomarkers	CPK b , CPK-MB b , Troponin I and/or hs Troponin T, hsCRP c , LDH
		Hematology	
		Glucose	Fingerstick
4	72 hours postdose	Glucose	Fingerstick
7		Chemistry a	
		Hematology	
		Coagulation	

Day	Time (hours)	Panel	Comment
		Additional biomarkers	CPK b , CPK-MB b , Troponin I and/or hs Troponin T, hsCRP c , LDH
		Urinalysis	
15		Chemistry a	
		Hematology	
		Coagulation	
		Additional biomarkers	CPK b , CPK-MB b , Troponin I and/or hs Troponin T, hsCRP c , LDH
		Urinalysis	
30		Chemistry a	
		Hematology	
		Coagulation	
		Additional biomarkers	CPK b , CPK-MB b , Troponin I c and/or hs Troponin T c , hsCRP c , LDH
60		Chemistry a	
		Hematology	

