Day 2 (24 hours from EoI)	Exploratory biomarkers a / PK
Day 3 (48 hours from EoI)	PK
Day 4 (72 hours from EoI)	PK / Immunogenicity
Day 7	Exploratory biomarkers a / PK / Immunogenicity
Day 11	PK
Day 15	Exploratory biomarkers a / PK / Immunogenicity
Day 22	PK
Day 30	Exploratory biomarkers a / PK / Immunogenicity
Day 60	Exploratory biomarkers a / PK
Day 90	Exploratory biomarkers a / Immunogenicity
Day 135	Exploratory biomarkers a
Day 180 / End of Study Visit	Exploratory biomarkers a / Immunogenicity

Abbreviations: EOI, end of infusion; PK, pharmacokinetics

a BNP, hsCRP, NT-proBNP, Troponin I, hs Troponin T

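### SAP Section X applies the central-laboratory visit list to local results too, so its named visits omit 4 of the 5 local post-dose cardiac-panel samples scheduled in the first 48 hours

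*SAP*

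**What the plan says.** **SAP Section X** covers hsCRP, troponin I or hs-troponin T, CPK, CPK-MB, LDH, NT-proBNP and BNP. It states that "The analysis of exploratory biomarkers will be performed using the exploratory PD/biomarker evaluation population", with observed values and change from baseline summarized "by treatment groups and visits (Day 1 pre-infusion, Day 2, 7, 15, 30, 60, 90, 135, 180" (or end of study). Baseline is the Day 1 pre-infusion value. It then adds: "Separate summaries will be produced for results collected by Local labs (in the EDC system) and by Central labs". No second visit list is given for the local results.

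**Protocol 8.8** gives the sampling two roles: "Collection of samples for biomarker research is a component of the safety monitoring for this study and also an exploratory part of this study". It puts hsCRP, troponin, CPK, CPK-MB and LDH in a group called additional biomarkers, apart from "Exploratory biomarkers: NT-proBNP, total BNP".

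**Protocol Appendix 3** lists the additional biomarkers in Table 13 under the title "Protocol-required Safety Laboratory Assessments". Their local draw times are in Table 14, "Schedule of Protocol-required Safety Laboratory Assessments Performed by the Local Laboratory". Footnote l to Table 1 describes the Day 1 draws as being for safety. Table 15 gives the central-laboratory schedule, and its footnote a defines the central panel as "BNP, hsCRP, NT-proBNP, Troponin I, hs Troponin T".

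**Other analysis text.** Protocol 9.4.4 and SAP IX.A both call for biomarker summaries by treatment at scheduled time points, and IX.A refers to Protocol Section 1.3 for those times. SAP VII.C, the safety laboratory section, names hematology, chemistry, coagulation and urinalysis from local laboratories. The SAP's Changes from Protocol section mentions only abnormal vital signs.

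**The concern.** The protocol draws the local cardiac panel most densely in the 48-hour inpatient window and labels those draws as safety work. The only SAP section that names the panel for summary by dose group lists visits that skip most of them. A programmer working from Section X would tabulate 24 hours and nothing else between dosing and Day 7. The same vendor carries out IX.A and X, so it holds two different instructions for the same data.

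What is at stake is the end-of-study comparison of early troponin, CPK, CPK-MB, hsCRP and LDH changes between each JK07 dose and pooled placebo. Adverse-event tables do not replace it. Protocol 8.3.7 says laboratory abnormalities that the investigator does not judge clinically significant are not reported as adverse events, so a modest shift across a dose group could be absent from them.

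**Working it through.** The plan states no figure to reproduce. The check compares three schedules.

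| Post-dose time | Local panel (Table 14) | Central biomarkers (Table 15) | SAP Section X visits |
|---|---|---|---|
| 4 h | yes | no | no |
| 8 h | yes | no | no |
| 12 h | yes | no | no |
| 24 h (Day 2) | yes | yes | yes |
| 48 h (Day 3) | yes | no | no |
| Days 7, 15, 30, 60, 90, 135, 180 | yes (7) | yes (7) | yes (7) |
| **Total** | **12** | **8** | **8** |

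1. **Origin of the list.** The Section X visits, including Day 1 pre-infusion, are the same as the Table 15 biomarker visits, with none added or missing. The list fits the central data. It does not fit the local data to which Section X also applies it.

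2. **First 48 hours.** There are 5 local post-dose samples: 4, 8, 12, 24 and 48 h. Section X names 1 (24 h). Not named: 5 − 1 = 4, and 4/5 = 80%. The pre-dose sample is in the list. If it is counted, the figure is 4 of 6.

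3. **Whole study.** 12 local post-dose samples, 8 named, 12 − 8 = 4 not named, and 4/12 = 33%.

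4. **Can central samples fill the gap?** Table 13's additional biomarkers are CPK, CPK-MB, hs-troponin T, hsCRP, troponin I and LDH, which is 6 analytes. Table 15's footnote includes hsCRP and both troponins. CPK, CPK-MB and LDH (3 of 6) are therefore local only. At 4, 8, 12 and 48 h there is no central biomarker sample for any of the six.

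5. **Does other text settle it?**
   - SAP IX.A points to Protocol Section 1.3. Table 1 there marks the panel on Day 3, and footnote l gives 4, 8 and 12 h. Read alone, IX.A includes all four samples. Read alone, Section X does not.
   - SAP VII.C summarizes each scheduled visit and time point, so it would include them if the panel were within its scope. Its opening definition does not name the panel, and Table 13 keeps additional biomarkers in a row apart from clinical chemistry.
   - Protocol 9.4.3 asks for all laboratory results to be summarized by treatment group, but SAP I.B says the SAP takes precedence over the protocol.

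**The case against.** The strongest reply is that the samples are already covered. IX.A commits to scheduled time points, Section X does not say its visits are the only ones, and VII.C introduces its scope with the word include and promises shift tables for all laboratory tests. The table shells, which would show the actual time points, are in a separate document. This stands in part: it turns an omission into an inconsistency. It does not remove the problem, because an explicit list that covers local results will usually be followed over a general cross-reference.

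A second reply concerns value. Sites may run troponin I or hs-troponin T, and CPK or CPK-MB may go unmeasured under the footnotes to Tables 13 and 14. Local dose-group means will rest on few subjects and may mix assays. This stands as a limit on the proposed tables, and it is why the two troponins should be kept apart.

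Some stronger readings are tempting but are not supported:

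- *The data are lost or safety oversight fails.* SAP Section X lists the results, investigators review laboratory reports (Protocol 8.2.7), and the Data Review Committee reviews safety before each escalation (Protocol 9.6).
- *The SAP demoted a safety endpoint.* The protocol itself makes biomarkers an exploratory endpoint, gives them a deviation-filtered analysis set (Table 11), and leaves the panel out of the primary laboratory endpoint.
- *The PD/biomarker set will remove dosed subjects from the panel's safety reading.* Its exclusion criteria are left to blinded review, and nothing in the documents says how likely an exclusion is.
- *The monkey troponin findings point to the first 48 hours.* Protocol 4.2 places the increases on Day 8 (10 and 30 mg/kg) and Day 28 (30 mg/kg) in a repeat-dose study, nearer to visits that Section X does name. By the scaling in Protocol 4.3, 10 mg/kg is 10 × 0.97/3 = 3.2 mg/kg in humans, above the 2.5 mg/kg cap. The case for the early samples rests on the protocol's own decision to draw them for safety.

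**Conclusion.** The point holds as an inconsistency in the SAP with a specific consequence. If Section X is followed as written, its dose-group tables show 1 of the 5 local post-dose panel samples in the first 48 hours and 8 of the 12 over the study. For CPK, CPK-MB and LDH, Section X's local summary is the only dose-group summary that names them. If IX.A is followed instead, nothing is missing, and the SAP does not say which section governs.

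This assumes that Section X's visit list is meant to be complete and that the unseen table shells do not correct it. The effect is on end-of-study reporting in a descriptive trial. It does not touch data collection or dose-escalation decisions.

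**What to change.** 1. In SAP Section X, state that the visit list applies to central-laboratory results (the Table 15 schedule). Keep the PD/biomarker population there for the exploratory reading.
2. In SAP VII.C, add the local panel: troponin I and hs-troponin T summarized separately by assay, CPK, CPK-MB, hsCRP and LDH. Give observed values and change from baseline by treatment group at every Table 14 time point, including 4, 8 and 12 h on Day 1 and 48 h on Day 3.
3. State that these tables use all dosed subjects. The words matter because SAP V.K defines the Safety Evaluation Population through randomization, and sentinel subjects are not randomized.
4. Align IX.A with these two statements.

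The cost is a few sentences of SAP text and one extra set of descriptive tables from data already collected, with no new samples. The downside is that the tables will have small groups and site-dependent assays, so each should show the number of subjects measured at each time point and be read alongside the listings.
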